Study Protocol and Statistical Analysis Plan

STELLA-FTD: Examination of a Behavior Change Intervention for FTD Family Care Partners

[NCT ID not yet assigned] Unique Protocol ID: 26023

10/20/2023

Minimal Risk Protocol Template

1) Protocol Title

STELLA-FTD: Examination of a Behavior Change Intervention for FTD Family Care Partners

2) Objectives

The purpose of this study is to test the STELLA-FTD intervention that we designed from our pilot study, STELLA-FTD, Phases 1 and 2. The STELLA (Support via Telehealth: Living and Learning with Advancing Alzheimer's Disease)-FTD intervention to specifically address the needs of family care partners of persons with frontotemporal degeneration (FTD). STELLA-FTD is a multicomponent video-conference based intervention designed to facilitate effective use of community and peer resources to foster effective management of behavioral and psychological symptoms of dementia. In the STELLA-FTD intervention, professionals ("Guides") meet with family members ("Care Partners") caring for persons with FTD conditions. Working together, the Care Partners and Guides identify strategies to address upsetting behaviors. The goal of this intervention is to reduce upsetting behaviors and thus care partner burden. **In this study, we will test STELLA-FTD, to specifically address the needs of family Care Partners for persons with frontotemporal degeneration.**

The Specific Aims are:

Aim 1: Test the preliminary efficacy of STELLA-FTD in this **NIH Stage 1B** ⁽¹⁾ clinical trial by comparing burden on the primary outcome measure, *reactivity* on the Revised Memory and Behavior Problems Checklist (RMBPC)⁽²⁾, between two care partner groups: the test group, who receives training in the ABC analytic approach and the control group that does not.

H0: There will be no change on the RMPBC reactivity score in the two pre-intervention assessments (completed at weeks 1 and 4) in both test and control groups.

H1: Upon completion of the STELLA-FTD intervention, care partners in the test group will have significantly lower (better) burden scores than those in the control group.

[figure not shown]
Aim 2: Test the **mechanism of action** of STELLA-FTD by isolating the ABC training component (the behavior change technique) and determining its relationship to self-efficacy ⁽³⁾ (the intervention target) and burden (the primary outcome) ⁽²⁾ (Figure A).

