In Teri et al. ⁽³⁰⁾ the differences in RMBPC reactivity scores ⁽²⁾ between baseline and post-intervention visit were -1.6(SD=7.6) with an effect size of 0.21 in care partners in the control group (routine medical care), and -5.8(SD=9.8) with an effect size of 0.59 in care partners in the intervention group (the ABC group). The effect size of difference in change in RMBPC ⁽²⁾ reactivity score between the two groups was 0.38. Based on this study, we conservatively determined the sample size calculation with an effect size of difference in pre-post intervention change as 0.3. To achieve at least 80% power to detect such a difference in a study design with three repeated measurements and an Intra-Class Correlation (ICC) =0.5 to 0.6 in compound symmetry covariance structure, we need at least 117 to 128 subjects/each group, for alpha = 0.05.

We anticipate an increase in power due to our conservative approach, e.g., based on three time repeated measures instead of 6 time points (Figure 2) and smaller effect size between intervention

and control groups on the RMBPC (compared to 0.59 Teri et al.)⁽³⁰⁾. We will use this increase in power to compensate for the complexity of the proposed model when adjusting covariates are taken into consideration. For self-efficacy, based on estimates from the STELLA-FTD pilot, group sample sizes of 128 will achieve 80% power to detect a difference of 0.32 at alpha level of 0.05, which is reasonable given pilot data trends⁽⁴²⁾.

In determining the sample size, we took attrition into account. Based on our experience⁽²⁹⁾, it is likely that up to 15% of the sample will withdraw due to schedule demands, illness and death, thus we will over-recruit to enroll 300 care partners.

5) Study Population

a) Number of Subjects

Participants. Informed by our power analysis, we will enroll a total sample of 600 participants: 300 family care partners and their 300 care recipients with FTD. For our study “family care partner” includes any person who is considered “family” to the person with FTD, such as direct relations, fictive kin, close friends and neighbors. “Care recipient” is defined as an individual with an FTD diagnosis: bv-FTD, PPA, progressive supranuclear palsy (PSP), corticobasal degeneration (CBD), or FTD with motor neuron disease⁽⁴³⁾.

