Data from this study may be shared with other investigators for future research studies through the data repository (OHSU IRB # 6845). Data from the repository will be shared with other investigators according to the IRB approved repository policy.

8) Data Analysis

Data Analysis. This study will generate a comprehensive set of data that tests STELLA-FTD's preliminary efficacy and its mechanism of action. In all final models, we will examine the relationships between diagnosis type, demographic and biological characteristics (e.g., sex, race, education) and the outcome and process variables.

Aim 1. Test the preliminary efficacy of STELLA-FTD in this NIH Stage 1B clinical trial by comparing burden (reactivity on the RMBPC (2)), between two care partner groups: the test group, who receives training in the ABC analytic approach and the control group that does not.

H0: There will be no change on the RMPBC reactivity score in the two pre-intervention assessments (completed at weeks 1 and 4) in both test and control groups. The primary outcome for H0 is the RMBPC (2) reactivity score. First, we will provide both statistical and graphical evaluation for the distributions of the primary outcome and transform the data to normalized values if needed (e.g., log transformation). We will descriptively explore the RMBPC (2) reactivity score at weeks 1 and 4 for each group and the primary outcome will be reported as mean (SD). To test whether reactivity scores change from week 1 to week 4, paired t-tests will be used to compare scores within each group. Then, we will compute the change scores between week 1 and week 4 for each participant and the normality of change score will be assessed. If normality assumption is violated, we will perform a data transformation. To test the difference in change scores between weeks 1 and 4, we will conduct a two-sample t-test of the change score between the test and control groups. All of the results will be considered significant at $\alpha = 0.05$. We expect no significant change between weeks 1 and 4 within each group and the change scores will not be significantly different between the test group and control group.

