H1: Upon completion of the STELLA-FTD 8-week intervention, care partners in the test group will have significantly lower (better) burden scores than those in the control group. For H1, we will employ a mixed effects model to analyze whether the change in reactivity on the RMBPC (2) differs across groups (test vs. control) over the intervention period. Two fixed effects will be included in the model: 1) Group effect will be included as a dichotomous categorical variable (test vs. control); 2) Time effect will be included as a continuous variable. The interaction between group and time (group x time) will also be included. Random intercepts will be incorporated for subject specificity in the model to account for clustering effect within subject over time. We will perform a hypothesis test for the coefficient of the interaction term (group x time) to assess the difference in change on primary outcome in the intervention group as compared to control group, over time. We will extend the model to include diagnosis type (e.g., PPA, bv-FTD), frequency of behavioral symptoms as measured on the RMBPC (2), socio-demographic covariates (e.g. sex, age, sex, education) and external support group use. Results will be considered significant at $\alpha = 0.05$, with two-sided test. Similar analyses will occur at Week 20 and 36.

Aim 2. Test the mechanism of action of STELLA-FTD by isolating the ABC training component (the behavior change technique) and determining its relationship to self-efficacy (the intervention target) and burden (the primary outcome) (Figure A).

The statistical analyses for Aim 2 will be carried out in three steps to investigate the mediated effect of self-efficacy ⁽³⁾ on the association between intervention and primary outcome, the RMBPC ⁽²⁾ reactivity score.

H2: Care partners who receive STELLA-FTD with ABC training (the test group) will have significantly higher self-efficacy scores ⁽³⁾ than the control group. To test H2 in the first step, we will employ a similar mixed effect model as H1. The mixed effect model analyses will be performed on total self-efficacy score as the outcome. A hypothesis test for the coefficient of the interaction term (group x time) will be performed to assess the difference in change on self-efficacy score in the test group as compared to control group, over time.

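### Aim 1 H0 claims no change between weeks 1 and 4, but non-significant difference tests with no margin cannot support that claim

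*Combined protocol and SAP*

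**What the plan says.** Section 2 (Objectives) and section 8 (Data Analysis, Aim 1) both state the hypothesis, labelled H0, on the primary outcome measure: "There will be no change on the RMPBC reactivity score in the two pre-intervention assessments". It applies to both groups.

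Section 8 gives the analysis:

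- Scores are summarised as mean (SD) at each week, by group.
- Within groups, "paired t-tests will be used to compare scores within each group".
- Between groups, "we will conduct a two-sample t-test of the change score between the test and control groups".
- On the threshold, "All of the results will be considered significant at" 0.05. Sidedness is not stated here; H1 is specified "with two-sided test".
- The anticipated result is "We expect no significant change between weeks 1 and 4 within each group and the change scores will not be significantly different".

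There is no equivalence margin, no confidence interval for the change, and no power or precision figure for these tests. The plan does not say what follows if one of them is significant. The sample size in section 4 is built on a different quantity, an "effect size of difference in pre-post intervention change as 0.3".

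**The concern.** Here the claim to be supported is the null hypothesis itself. A difference test can reject it but cannot confirm it: a non-significant result may mean a stable score or an estimate too imprecise to show a drift. The conclusion on H0 can therefore go wrong in two ways. A real drift may pass unnoticed and be reported as stability, or a stable score may give an isolated significant result that contradicts the stated expectation by chance. What is at stake is the statement the trial will make about this Aim 1 hypothesis.

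**Working it through.** **Inputs.** From section 4 (sample size calculation): effect 0.3, three measurements, ICC 0.5 to 0.6 under compound symmetry, 80% power, alpha 0.05, 117 to 128 per group, up to 15% withdrawal, 300 enrolled. Assumed: two-sided tests and 1:1 allocation, so 300/2 = 150 per arm at enrolment and 150 × 0.85 = 127.5, about 128, after the full planned loss. Drifts and margins are in units of the SD of a single reactivity score. The 0.15 SD drift is an illustration, not a figure from the plan.

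**1. The plan's own figure.** n = 2(1.96 + 0.8416)² × [(1 + 2·ICC)/3] / 0.3².
- ICC 0.5: 2 × 7.849 × 0.6667 / 0.09 = 116.3, so 117.
- ICC 0.6: 2 × 7.849 × 0.7333 / 0.09 = 127.9, so 128.

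Both reproduce. They concern the group comparison, not H0.

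**2. Precision of the week 1 to week 4 change.** SD of change = √(2(1 − ICC)) = 1.000 at ICC 0.5 and 0.894 at ICC 0.6. At 128 per arm, the 95% half-widths are:
- within an arm, 1.96 × SD/√128 = 0.173 and 0.155;
- between arms, 1.96 × SD × √(2/128) = 0.245 and 0.219.

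**3. Chance of missing a true 0.15 SD.** Miss rate = Φ(1.96 − 0.15/SE) − Φ(−1.96 − 0.15/SE). For example, within an arm at 128 and ICC 0.5, SE = 0.0884, 0.15/SE = 1.70, and the miss rate is 60%.

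| Comparison | n per arm | ICC 0.5 | ICC 0.6 |
|---|---|---|---|
| Within arm | 128 | 60% | 52% |
| Within arm | 150 | 55% | 46% |
| Between arms | 128 | 78% | 73% |
| Between arms | 150 | 75% | 69% |

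**4. Perfect stability.** The two paired tests are independent of each other, and the two-sample test uses the same changes. Simulating two independent standard normal statistics and their scaled difference, all three are non-significant about 89% of the time. At least one is significant about 11% of the time.

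**5. What a margin rule would deliver.** With no true drift, the chance that the 90% CI lies within ±M is 2Φ(M/SE − 1.645) − 1 in one arm, and its square in both arms. At 128 per arm (lower figure ICC 0.5, upper figure ICC 0.6):

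| Margin (assumed) | One arm | Both arms |
|---|---|---|
| ±0.30 SD | 92% to 97% | 85% to 94% |
| ±0.20 SD | 46% to 62% | 21% to 39% |
| ±0.15 SD | 4% to 20% | 0.2% to 4% |

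**The case against.** The strongest reply is that nothing important depends on H0. H1 is a randomised group-by-time comparison that is not conditional on H0, and section 4 credits the effect of ABC training to the comparison between groups. Drift common to both arms goes into the time term, not the interaction. This stands. A reader might infer that the double baseline is what allows later change to be credited to the intervention, so that a faulty H0 check undermines the efficacy result. The documents state no such rationale.

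Second, the 0.3 in section 4 is a between-group difference. A within-arm drift of 0.15 SD is therefore not half of the planned effect in any sense that biases it. This also stands; only the between-arm figures are on the same footing as the 0.3.

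Third, the plan states an expectation, not a decision rule. It does not say that one significant test means instability, so the 11% is the chance that the expected pattern fails to appear, not a planned error rate. The plan also reports means and SDs, so p-values are not its only output. Even so, non-significance is the only criterion it offers for its hypothesis.

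Fourth, a reader might infer that the trial is too small for this check. The figures do not support that: at a margin of ±0.30 SD, 128 per arm would usually suffice within each arm. The missing margin is the fault.

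**Conclusion.** The concern holds, limited to H0. The plan sets out a hypothesis of no change and offers as support only the absence of significance, which cannot establish it at any sample size. At the plan's own ICC, a within-arm drift of 0.15 SD would more often than not be missed at 128 per arm, and about half the time at 150; both assessments precede the sessions, so the larger number may be available. The same difference between arms would be missed about seven times in ten or more at either size. The primary H1 comparison is unaffected. These figures rest on two-sided tests, 1:1 allocation, compound symmetry and the illustrative 0.15 SD; the logical point rests on none of them.

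**What to change.** In section 8, Aim 1, H0, replace the three significance tests with the mean week 1 to week 4 change in each arm and the between-arm difference, each with a confidence interval. State that non-significance will not be described as stability. Then choose one of two options:

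- Claim stability only if the 90% CI in each arm lies within a margin that the sponsor fixes before the data are seen, and otherwise report the result as inconclusive.
- Label the check descriptive and make no claim of stability.

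The change is to SAP wording and needs no new data. Its price is a possible inconclusive result even when scores are stable. That risk is modest at ±0.30 SD. At ±0.20 SD, both arms together would more often be inconclusive than not at 128 per arm. A margin as tight as ±0.15 SD is nearly unattainable at that size. All three margins are assumptions used to show the trade-off.

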Delivery monitoring. All STELLA-FTD sessions will be recorded and recordings will be stored on a secure server that the fidelity assessment team can access via the OHSU secure filesharing system. The team will view a randomly-identified subsample (15%) of the recordings to evaluate procedural, documentation and theoretical fidelity. Fidelity items are scored using a binary rating of "1" (present) or "0" (absent), with clearly defined characteristics required for either rating. Inter-rater agreement on video assessments will be measured (62).

Standardized checklists and criteria will be used for each fidelity domain. Guides will be required to complete session content checklists to ensure essential study components are addressed. Session duration will be monitored to prevent potential threats of variance in dosing between trial groups.

We will actively monitor for potential contamination between the test and control groups. Our study design, operationalized procedures and ongoing and diligent fidelity monitoring will aid in early identification and management of fidelity concerns (60).

Taken together, the STELLA-FTD intervention will be implemented within an adequately-powered research design that will test the proposed hypotheses. We will have a fidelity assessment process in place to ensure adherence to protocol. Our intervention will allow us to conduct the trial efficiently and provide interpretable results. To answer our research questions, we will employ relevant measures.

Anticipated challenges. Scheduling Care Partners may be difficult. Thus, the protocol allows the following concessions:

- The study team may alter the session schedules due to holidays, illness or other scheduling issues.
- There may be two sessions may be doubled in a week if scheduling challenges.
- Care Partners can skip up to 3 sessions and still remain in the study.
- If there are more Care Partners than available Guides, the Care Partners may have to wait to the sessions. We will enroll them and have them do the weekly survey until there is space. Four weeks prior to start, they will complete their first set of surveys.

Table 2: STELLA-FTD Care Partner Activities

Activity	Description	Due
Consent	Care Partner and care recipient consent	Prior to any study activities
Randomized to groups	Either test or control group	After consent completed
Assessments	Baseline Assessment	4 weeks prior to STELLA-FTD start

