Assessments	Pre-Intervention Assessment	1 week prior to STELLA-FTD start
STELLA-FTD Intervention	Meet with Faculty and Guest Speakers for 8 weekly, 1-hour, sessions	1 week after pre-intervention assessment
Assessment	Mid-intervention Assessment	4 weeks after start of STELLA-FTD sessions
Assessment	Post Assessment 1	Within one week of completion of STELLA-FTD
Assessment	Post-Assessment 2	2 months after end of STELLA-FTD
Assessment	Post-Assessment 3	6 months after end of STELLA-FTD
Weekly Orbit Surveys: Distributed weekly		
Orbit surveys start after enrollment and continue until all surveys are completed		

Measures (Table 3). The primary outcome variable, burden, will be assessed with the 24-item RMBPC (2), which measures the frequency of care recipient behavioral symptoms and care partner reactions to these behaviors. The RMBPC was chosen because it aligns with our theoretical foundation that assumes burden is a result of care partner reactions to behavioral symptoms. The RMBPC has been used in Teri's work (30) and our telehealth

studies, (29, 31, 33, 34) including the STELLA-FTD pilot, allowing for comparison across studies.

Self-efficacy, the mediating variable, will be assessed using Fortinsky's measurement of family care partner self-efficacy for managing dementia (3). We considered the other measures, but Fortinsky's assesses the targets in STELLA-FTD: behavior symptom management and service use.

We will measure care partner preparedness for current and future challenges (63) and personality type to test the effect of a group-based intervention (64).

For care partners in STELLA-FTD+ABC, we will assess the results of the care partners' personalized ABC plans prior to and after the 8-week intervention by collecting data on the frequency of their identified behaviors, and their reactions to them, on their Personalized Target Behavior Survey (29, 30). We will collect data on number of ABC plans each care partner writes on the Orbit weekly survey, weeks 4-36.

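### The 117 to 128 per group is sized for an average over three visits, but H1 tests a group-by-time slope that has about 67–77% power and no named visits

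*Combined protocol and SAP*

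**What the plan says.** H1 in Section 8 is worded as a group difference in burden once the intervention is finished. The analysis asks "whether the change in reactivity on the RMBPC (2) differs across groups (test vs. control) over the intervention period". The model has group, time and their interaction. "Time effect will be included as a continuous variable", and "Random intercepts will be incorporated for subject specificity in the model". The interaction coefficient is the test, two-sided at 0.05. The covariates listed for the extended model do not include baseline reactivity. For the later visits the text says only "Similar analyses will occur at Week 20 and 36".

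The sample size paragraph in Section 4 takes an "effect size of difference in pre-post intervention change as 0.3", assumes three repeated measurements with an ICC of 0.5 to 0.6, and concludes that "in compound symmetry covariance structure, we need at least 117 to 128 subjects/each group". Enrolment is 300, to allow for 15% attrition.

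Table 3 places the primary measure at weeks 1, 4 and 8 and at Post Assessments 1 to 3. Post Assessment 1 has no week number; Table 2 times it "Within one week of completion of STELLA-FTD". Section 6 (Anticipated challenges) also allows the session calendar to shift: "There may be two sessions may be doubled in a week if scheduling challenges".

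**The concern.** The sample size and the test do not belong together. A difference averaged over visits and a difference in change over time respond to the ICC in opposite ways. Under compound symmetry, a higher ICC makes an average less precise and a within-person change more precise. The plan's N rises with the ICC, from 117 to 128. For a change or slope test it should fall, or stay level if the effect is expressed in SD-of-change units.

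The H1 text also leaves the visit set open. The primary measure is taken twice before the intervention, and H0 expects no movement between those two scores. If week 1 enters the slope, one straight line is fitted across a flat run-in and the treatment period. Power and the size of the estimate then depend on a choice that can still be made after the data are seen. H2 uses a similar model and H4 extends H1, so the ambiguity carries into the mechanism analyses.

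**Working it through.** **Inputs.** From Section 4: effect 0.3, three measures, compound symmetry, ICC ρ = 0.5 to 0.6, alpha 0.05, 80% power. H1 states a two-sided test. Completers per group: 300 × 0.85 / 2 = 127.5, taken as 128. K = (1.960 + 0.8416)² = 7.849. Post Assessment 1 is assumed to fall at week 12: Table 2 puts Post-Assessment 2 two months after the end, and H1 refers to week 20.

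**Units of 0.3.** The source effect sizes are changes divided by the SD of change: 1.6/7.6 = 0.21 and 5.8/9.8 = 0.59, a difference of 0.38. This points to SD-of-change units. Under compound symmetry the SD of change is √(2(1−ρ)) = 1.000 or 0.894 outcome SDs, so 0.3 becomes 0.300 or 0.268 outcome SDs. Both readings are carried below.

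**1. The plan's own figure.** For a difference averaged over three measures, n = 2K × [(1+2ρ)/3] / 0.3².
- ρ = 0.5: 2 × 7.849 × 0.6667 / 0.09 = 116.3, so 117.
- ρ = 0.6: 2 × 7.849 × 0.7333 / 0.09 = 127.9, so 128.

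Both ends match. Endpoint change, a single post visit, baseline-adjusted and several-post-visit formulas were also tried, and none matches both ends.

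**2. The test H1 specifies, on weeks 4/8/12.** With equal spacing and complete data, the slope over 8 weeks equals the week 4-to-12 change, whatever happens at week 8. So n = 2K × 2(1−ρ) / δ² and power = Φ(δ / √(4(1−ρ)/128) − 1.96).
- Outcome-SD units, ρ = 0.5: n = 174.4; 0.3/0.125 = 2.40; power 67.0%.
- Outcome-SD units, ρ = 0.6: n = 139.5; 0.3/0.1118 = 2.68; power 76.5%.
- SD-of-change units, either ρ: n = 174.4; power 67.0%.

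At the plan's lower pairing (117 per group, ρ = 0.5) power is 63.1%. If the groups differed by a constant 0.3 at all three visits, as the averaging formula assumes, the slope difference would be zero and the test would reject only at its alpha level.

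**3. If week 1 is added.** The slope-implied week 4-to-12 change, as a fraction of the true change, and power at 128 per group:

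| Effect at weeks 1, 4, 8, 12 | Fraction of true change | Power, ρ = 0.5 (also SD-of-change units at either ρ) | Power, ρ = 0.6, outcome SD |
|---|---|---|---|
| 0, 0, ½, 1 | 0.771 | 77.4% | 85.8% |
| 0, 0, 1, 1 | 0.873 | 86.7% | 93.0% |
| 0, 0, 0, 1 | 0.669 | 65.3% | 74.9% |

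**4. Adjusted contrast at Post Assessment 1.** Residual variance is 1−ρ² = 0.75 / 0.64 with week 4 as covariate, and 1−2ρ²/(1+ρ) = 0.667 / 0.55 with weeks 1 and 4. Values are for ρ = 0.5 / 0.6:

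| Covariates | Power, SD-of-change | Power, outcome SD |
|---|---|---|
| Week 4 | 79.1 / 76.5% | 79.1 / 85.1% |
| Weeks 1 and 4 | 83.6 / 82.5% | 83.6 / 89.9% |

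With both baselines, 80% power needs 116.3 / 119.9 per group (SD-of-change) or 116.3 / 95.9 (outcome SD).

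**5. Sensitivity.**
- Visit timing: with the mid visit at week 8 or 9 and the post visit at weeks 11 to 13, the three-visit slope gives 90–106% of the true change.
- Correlation: under compound symmetry the type I error is 5%. If correlation instead decays serially (an assumption made here, AR(1) with 0.5–0.6 at 8 weeks), the random-intercept test rejects a true null about 10% of the time on weeks 4/8/12 and 15% on weeks 1/4/8/12. The second baseline then adds nothing, and the adjusted contrast has 77–79% power (SD-of-change) or 79–85% (outcome SD). The three-visit slope with a valid standard error has 67% or 67–77%.
- Simulation, 6,000 trials per setting, outcome-SD units, ρ = 0.5 / 0.6: three-visit slope 67.2 / 75.8%; two-baseline contrast 82.5 / 89.0%; type I error under compound symmetry 5.1–5.5%.

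**The case against.** The text does point to one visit set. H1 is limited to the intervention period, the sample size speaks of three measurements, and weeks 1 and 4 have their own tests under H0. Pre, mid and post is therefore the natural reading, and on it the slope is an unbiased estimate of the difference in change. The week 4 score enters as a response, so leaving it out of the covariates costs precision and not validity. All of this stands, and it makes the week 1 figures secondary. An explicit visit list is still missing.

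The shortfall also rests on cautious planning values. With no attrition (150 per group) the slope has 73.8% power, or 82.8% in outcome-SD units at ICC 0.6. At the source study's 0.38 it has 86–92%. Standardising the source's difference in change by the pooled SD gives 4.2/8.77 = 0.48 and about 97%. But 0.3 and 15% attrition are the values the plan chose, and its 80% claim is made at those values. Section 4 also expects a reserve from six time points. A six-visit slope would reach 83–90% in outcome-SD units if 0.3 were held from week 12, but the later visits lie outside the period H1 covers.

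The inflated type I error depends on an assumed serial correlation that the plan does not make, so it supports a safer covariance without showing an error.

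The replacement contrast has modest headroom. An assumed ICC of 0.02 within sessions of 8 gives a design effect of 1 + 7 × 0.02 = 1.14, which would bring the two-baseline contrast to 77–79% in SD-of-change units. It would bring the slope to 61%, so the ranking does not change.

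**Conclusion.** The concern holds. The stated sample size is for a different test from the one H1 performs. At the plan's own values and 128 per group, H1 on weeks 4/8/12 has 67% power in the units the text points to and 67–77% in outcome-SD units. It would miss the planned effect in 23–33% of trials where the plan intends 20%. The required number is 140 to 175 per group.

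These figures assume complete data, compound symmetry, independent participants, no covariates and Post Assessment 1 at week 12. They are normal approximations, supported by simulation. The missing visit list matters because adding week 1 moves power to anywhere from 65% to 93% and shrinks the implied week 4-to-12 effect to 67–87% of its true size. This should be settled before any outcome data are examined.

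**What to change.** - List the visits that enter the H1 model.
- Make the primary test the group difference at Post Assessment 1, from a model with visit as a categorical factor. Use both pre-intervention scores, either as covariates or as responses constrained equal across groups.
- Use an unstructured within-person covariance, or robust standard errors.
- Define the week 20 and week 36 comparisons as separate secondary contrasts from the same model.
- Align H2 and H4 with this contrast. Table 3 does not measure self-efficacy at the mid-intervention visit, so their visit list will differ.
- Restate power for the test actually used, and say whether 0.3 is in outcome-SD or SD-of-change units.

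If the slope is kept, list its visits, use robust standard errors and restate its power.

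The change needs no new data. It estimates a few more parameters, a small burden with about 255 completers. It gives up some power relative to a four-visit slope if the effect is complete by week 8 and compound symmetry holds: 82–84% against 87% in SD-of-change units, or 84–90% against 87–93% in outcome-SD units.
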